7.2 Patient demographics/other baseline characteristics

Demographic data include: Date of birth, sex, and race.

Baseline characteristics include: Medical history/current medical condition, prior medication, tumor history, baseline tumor assessment, relevant prior tumor therapy, ECOG, vital signs (height, weight, blood pressure, pulse), result of pregnancy test, hematology and biochemistry.

HBV testing

Prior to starting study drug, the categories of patients listed in Section 4 Changes to Study design should be tested for hepatitis B serologic markers and viral load: HBV-DNA HBsAg, HBc Ab, and HBs Ab.

HBV DNA monitoring should be done depending on results from serologic markers and viral load as listed in Table 4.

HCV testing

Patients with hepatitis C risk factors and additional patients at the discretion of the investigator should be tested for HCV RNA-PCR test at baseline. For a list of hepatitis C risk factors, refer to Section 4 Changes to Study design.

Follow-up testing will be performed, as per the visit schedule, only if the patient has a history or is positive at baseline, or both.

7.3 Treatments

Study drug administration will be documented. Dose modifications and interruptions will be documented ongoing.

7.4 Efficacy

Tumor evaluation

Disease status will be based on CT/MRI scans and/or chest x-ray performed maximum ca. 2 weeks before baseline, thereafter after week 8, 16, 28, 40, 52 and X, respectively at final visit. If medically indicated, unscheduled CT/MRI examinations and/or chest x-ray will be performed at the investigator's discretion. Response status will be evaluated using RECIST criteria (please see Post-text supplement 1). The evaluation of the central radiologist will be used.

At baseline and 1st comparative FDG-PET assessment at visit 5 can be carried out optional in non-German-centers in order to provide this additional perspective on changes in tumor activity induced by the therapy and give data on correlation of PET as an indicator for progression or response. Although ¹⁸F-FDG-PET functional imaging may be valuable as a complement to standard anatomical imaging (CT or MRI) in any tumor assessment (identification of new lesions or of newly active foci in otherwise inactive lesions), the primary variable for efficacy assessment will be that obtained by standard anatomical imaging.

7.5 Safety

7.5.1 Adverse events

An adverse event is the appearance or worsening of any undesirable sign, symptom, or medical condition occurring after date of signed informed consent even if the event is not considered to be related to study drug. Study drug includes the investigational drug under evaluation that is given during any phase of the trial. Medical conditions/diseases present before date of signed informed consent are only considered adverse events if they worsen

after date of signed informed consent. Abnormal laboratory values or test results constitute adverse events only if they induce clinical signs or symptoms, are considered clinically significant, or require therapy (e.g. any hematologic abnormality that requires transfusion or cytokine treatment). In addition, abnormal laboratory values that cause study discontinuation or constitutes in and of itself a Serious Adverse Event (SAE) should be recorded on the Adverse Events CRF.

Adverse events will be assessed according to the Common Terminology Criteria for Adverse Events (CTCAE) version 3.0 (<http://ctep.cancer.gov/forms/CTCAEv3.pdf>). If CTCAE grading does not exist for an adverse event, the severity of mild, moderate, severe, and life-threatening, OR grades 1 – 4, will be used. **CTCAE grade 5 (death) will not be used in this study; rather, this information will be collected in the End of Treatment or Survival Information CRF page.** Adverse event monitoring should be continued for at least 4 weeks following the last dose of study drug.

The occurrence of adverse events should be sought by non-directive questioning of the patient at each visit during the study. Adverse events also may be detected when they are volunteered by the patient during or between visits or through physical examination, laboratory test, or other assessments. As far as possible, each adverse event should be evaluated to determine:

1. the severity grade (CTCAE Grade 1 – 4) or mild, moderate, severe, life-threatening if CTCAE grading does not exist for an adverse event,
2. its relationship to the study drug(s) (suspected/not suspected),
3. its duration (start and end dates or if continuing at final exam),
4. action taken (no action taken; study drug dosage adjusted/temporarily interrupted; study drug permanently discontinued due to this adverse event; concomitant medication taken; non-drug therapy given; hospitalization/prolonged hospitalization), and
5. whether it is serious, where a serious adverse event (SAE) is defined as one which:
 - is fatal or life-threatening
 - results in persistent or significant disability/incapacity
 - constitutes a congenital anomaly/birth defect
 - requires inpatient hospitalization or prolongation of existing hospitalization, unless hospitalization is for:
 - routine treatment or monitoring of the studied indication, not associated with any deterioration in condition (specify what this includes)
 - elective or pre-planned treatment for a pre-existing condition that is unrelated to the indication under study and has not worsened since the start of study drug
 - treatment on an emergency outpatient basis for an event not fulfilling any of the definitions of an SAE given above and not resulting in hospital admission
 - social reasons and respite care in the absence of any deterioration in the patient's general condition
 - is medically significant, i.e. defined as an event that jeopardizes the patient or may require medical or surgical intervention to prevent one of the outcomes listed above

In contrast to routine safety assessments, SAE are monitored continuously and have special reporting requirements; see Section 8.1 “Serious adverse event reporting”.

All adverse events should be treated appropriately. Such treatment may include changes in study drug treatment including possible interruption or discontinuation, starting or stopping concomitant treatments, changes in the frequency or nature of assessments, hospitalization, or any other medically required intervention. Once an adverse event is detected, it should be followed until its resolution, and assessment should be made at each visit (or more frequently, if necessary) of any changes in severity, the suspected relationship to the study drug, the interventions required to treat it, and the outcome.

Information about common side effects already known about the investigational drug can be found in the Investigator's Brochure or will be communicated between IB updates in the form of Investigator Notifications. This information will be included in the patient informed consent form and should be discussed with the patient during the study as needed.

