****This list of clinically relevant drug interactions is updated as of December 02, 2009****

6.3.6 Study drug discontinuation

Study drug must be discontinued for a given patient if the investigator determines that continuing it would result in a significant safety risk for that patient. Patients who, in the opinion of the investigator, require alternative medical therapy, will be discontinued from the study. Patients with a progression will be discontinued from the study. Patients who become pregnant during the study must be withdrawn. If the treatment has to be interrupted for more than 21 consecutive days for any reason, the patient will be discontinued from the study unless otherwise discussed with the study coordinator. In case of patient's discontinuation, the end of study evaluation will be completed as soon as possible. End of study evaluations will include adverse events, concomitant medications and therapies, physical examination, vital signs, ECOG performance status, biochemistry, hematology and tumor measurement.

Patients who discontinue prematurely due to significant AE should continue to be followed-up until resolution of the AE, and the relevant sections of the CRF should be completed as appropriate. Patients who are discontinued due to clinically significant abnormalities in clinical laboratory results should continue to be evaluated until the abnormality resolves or is judged to be permanent.

It will be documented whether or not each patient completed the clinical study. If, for any patient, the study treatment was discontinued the reason will be recorded. Reasons that a patient may discontinue participation in a clinical study are considered to constitute one of the following:

1. Adverse event(s)
2. Abnormal laboratory value(s)
3. Abnormal test procedure result(s)
4. Unsatisfactory therapeutic effect
5. Subject's condition no longer requires study treatment

6. Protocol violation which affect the safety of the patient
7. Subject withdraws consent
8. Lost to follow-up
9. Administrative problems
10. Death

Progressive disease is defined as unsatisfactory therapeutic effect.

For patients who are lost to follow-up, the investigator should show “due diligence” by documenting in the source documents steps taken to contact the patient, e.g. dates of telephone calls, registered letters, etc.

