It is agreed that for reasonable cause, either the investigator or Novartis may terminate this study, provided a written notice is submitted at a reasonable time in advance of the intended termination.

A Study Drug Discontinuation form should be completed, giving the date and primary reason for stopping the study drug.

Study treatment will be continued until progression. Patients will be followed until progression.

The overall survival will be documented on the survival information page for all patients except for those who withdrew consent or are lost to follow-up.

7 Visit schedule and assessments

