8.1 Serious adverse event reporting

8.1.1 Safety assessments

To ensure patient safety, every SAE, regardless of suspected causality, occurring after the patient has provided informed consent and until 4 weeks after the patient has stopped study participation (end of treatment) must be reported to Novartis within 24 hours of learning of its occurrence. Any SAE experienced after this 4-week period should only be reported to Novartis if the investigator suspects a causal relationship to the study drug. Recurrent episodes, complications, or progression of the initial SAE must be reported as follow-up to the original episode within 24 hours of the investigator receiving the follow-up information. An SAE occurring at a different time interval or otherwise considered completely unrelated to a previously reported one should be reported separately as a new event.

Information about all SAE is collected and recorded on the Serious Adverse Event Report Form. The investigator must assess the relationship to study drug, complete the SAE Report Form in English, and send the completed, signed form by fax within 24 hours to the local Novartis Clinical Safety & Epidemiology Department. The telephone and telefax number of the contact persons in the local department of Clinical Safety and Epidemiology, specific to the site, are listed in the Investigator Folder provided to each site. The original copy of the SAE Report Form and the fax confirmation sheet must be kept with the CRF documentation at the study site.

Follow-up information is sent to the same person to whom the original SAE Report Form was sent, using a new SAE Report Form stating that this is a follow-up to the previously reported SAE and giving the date of the original report. Each re-occurrence, complication, or progression of the original event should be reported as a follow-up to that event regardless of when it occurs. The follow-up information should describe whether the event has resolved or continues, if and how it was treated, and whether the patient continued or withdrew from study participation.

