1.5.2.1 Adverse events

Adverse events (AE) were summarized by presenting the number and percentage of patients having any adverse event, having an adverse event in each body system and having each individual adverse event. Furthermore, the incidence of AE was summarized by maximum severity, for AE with suspected drug relation, for serious AE, for AE leading to permanent discontinuation of study drug, and for significant AE. As significant (S)AE were defined those (S)AE who

- were suspected to be drug related,
- lead to dose adjustment or temporary interruption,
- lead to permanent discontinuation,
- required concomitant medication/non-drug therapy, and
- Deaths

Any other information collected (e.g. severity or relatedness to study medication) was listed as appropriate.

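### Progression of the study sarcoma counts as an adverse event under Protocol 7.5.1, and the SAP does not separate it, so serious-AE and discontinuation totals can mix progression with toxicity

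*Protocol*

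**What the plan says.** **Definition.** Protocol 7.5.1 opens broadly: "An adverse event is the appearance or worsening of any undesirable sign, symptom, or medical condition occurring after date of signed informed consent", whether or not the drug is suspected. For disease already present it adds: "Medical conditions/diseases present before date of signed informed consent are only considered adverse events if they worsen" after that date. Section 7.5.2 requires significant post-consent findings that meet the definition to be entered on the AE form.

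**Seriousness.** Also in 7.5.1, a fatal event is serious, and so is one that needs admission. Admission for the study disease is exempt only when it is for "routine treatment or monitoring of the studied indication, not associated with any deterioration in condition". Section 8.1.1 requires reporting of "every SAE, regardless of suspected causality, occurring after the patient has provided informed consent" up to 4 weeks after the end of treatment.

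**Stopping.** Protocol 6.3.6 takes patients off study at progression and states: "Progressive disease is defined as unsatisfactory therapeutic effect". That is a different item on its list of reasons from adverse events. The discontinuation form is completed "giving the date and primary reason for stopping the study drug". Separately, each AE record in 7.5.1 has an action field, and one option is permanent discontinuation because of that event.

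**Tables.** SAP 1.5.2.1 summarises AEs overall, by maximum severity, with suspected drug relation, serious, and "for AE leading to permanent discontinuation of study drug, and for significant AE". The significant category includes events suspected to be drug related, events that needed concomitant medication, and deaths.

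**The concern.** Every patient enters with progressive or metastatic sarcoma, so the sarcoma predates consent and its worsening falls inside the AE definition. The same event is a lack of effect on the discontinuation form. A site could reasonably follow either section, and neither document says which.

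Tolerability and safety is the first secondary objective listed, and no control arm shows how much of an event rate belongs to the disease. If progressions enter the serious, discontinuation and significant-AE tables, those totals rise as efficacy falls. A drug with little activity could then look poorly tolerated for reasons unrelated to its toxicity. Two sites with the same patients could also report different rates.

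**Working it through.** **Step 1: the text.**

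| Question | Answer in the documents |
|---|---|
| Is worsening of a pre-consent disease an AE? | Yes (Protocol 7.5.1) |
| Is the study sarcoma exempt? | No exemption in either document |
| Is admission with deterioration of the sarcoma exempt from being serious? | No; the exemption covers only admission without deterioration |
| Is progression an AE on the discontinuation form? | No; it is a separate reason (6.3.6) |
| Can an AE record reach the discontinuation-AE table by another route? | Yes; the action field on the AE record |
| Does SAP 1.5.2.1 separate progression? | No |
| Does it specify drug-suspected serious AEs, or drug-suspected AEs leading to discontinuation? | No; these summaries stand side by side and are not crossed |

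**Step 2: the pool of possible progressions.** The plan states no share of AEs due to progression, so there is no figure of its own to reproduce. The rates used below come from the design in Protocol 10.6, and that design does reproduce:
- n = 36 with at least 11 responders: type I error 8.89%, type II error 9.04% (stated 8.9% and 9.0%).
- n = 24 with at least 8 responders: 8.92% and 19.19% (stated 8.9% and 19.2%).

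Patients without disease control = n(1 − P), with P between 20% and 40%:
- Arm I: 36 × 0.6 = 21.6 to 36 × 0.8 = 28.8.
- Arm II: 24 × 0.6 = 14.4 to 24 × 0.8 = 19.2.

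**Step 3: the share of entries.** Let f be the fraction of these patients whose progression is entered as a serious AE or an AE leading to discontinuation. The documents do not give f. Let t be the toxicity rate. Protocol 1.3.3 gives 19% for severe, suspected drug-related, dose-limiting events in phase I. That is not a serious-AE or discontinuation rate and serves only as a proxy.

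Share = (1 − P)f / [(1 − P)f + t]. The sample size cancels. With t = 0.19:

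| f | P = 20% | P = 40% |
|---|---|---|
| 0% | 0% | 0% |
| 10% | 0.08/0.27 = 30% | 0.06/0.25 = 24% |
| 50% | 0.40/0.59 = 68% | 0.30/0.49 = 61% |
| 100% | 0.80/0.99 = 81% | 0.60/0.79 = 76% |

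Progression is more than half of the entries when f > t/(1 − P): 0.19/0.8 = 24% at P = 20% and 0.19/0.6 = 32% at P = 40%. For assumed t of 10% to 30%, the threshold runs from 12.5% to 37.5% at P = 20% and from 17% to 50% at P = 40%.

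The arithmetic counts entries and treats progression and toxicity as non-overlapping. It uses the week-16 design rates, so later events of either kind are left out.

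**The case against.** The documents contain real safeguards.
- Protocol 6.3.6 routes progression away from adverse events on the discontinuation form, and 5.2 and 6.3.1 list tumour progression apart from unacceptable toxicity.
- Under 7.5.1 an abnormal test result is an AE only if it causes symptoms, is clinically significant or needs therapy. Progression seen only on a scan is arguably a test result, so it need not become an AE.
- AEs are tabulated term by term in MedDRA, so a progression term would have its own line. Drug relation is recorded for each event, and the SAP has a table of suspected AEs.
- CTCAE grade 5 is not used; deaths are collected on other pages.
- All-causality AE reporting is a legitimate convention.

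Most of this stands, and it rules out three stronger readings.
1. A reader might infer that these tables will mainly measure lack of efficacy. That needs a value of f, and none is given.
2. A reader might add an assumed 10% of toxicity stops to 80–100% of the 60–80% primary failures and report a 58–90% rate of AEs leading to discontinuation. This assumes that nearly every failure is entered as such an AE, which is the open question. The 10% has no source in the documents. A patient who stops early for toxicity without stable disease is also a primary failure, so patients can be counted twice.
3. A reader might infer that two SAP tables must contradict each other. SAP 1.3 says only that permanent discontinuations are analysed by frequencies, not by reason. Primary reason for stopping and action taken for an AE are also different variables.

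The safeguards do not settle the totals. The discontinuation form does not govern the action field on the AE record. The suspected-AE table is not crossed with seriousness or discontinuation. An admission with deterioration remains serious, and fatal events and deaths remain within the serious and significant categories.

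**Conclusion.** The point holds as a gap in recording and display. Followed as written, 7.5.1 makes worsening of the study sarcoma an adverse event, 6.3.6 treats the same progression as something else, and SAP 1.5.2.1 does not tell the two apart. The serious, discontinuation and significant-AE totals can be substantially inflated by progression, but the documents do not show that they are. The range of 0% to about 80%, and the 24–32% threshold, rest on the phase I proxy for toxicity, the design values of P, no overlap between categories, and an unknown f. The primary conclusion, the type I error and the power are unaffected.

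**What to change.** In SAP 1.5.2.1, present the serious-AE, AE-leading-to-discontinuation and significant-AE tables in two forms: with all events, and without progression of, or death from, the sarcoma under study. Show each by suspected drug relation. List the progression events separately, and state which recording convention sites followed. Reconcile Protocol 7.5.1 with 6.3.6, so that the report says how one event comes to be classed under both.

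The change uses MedDRA terms and causality ratings that are already collected. Collection and reporting of AEs and SAEs stay unchanged. Enrolment is complete, so rewording 7.5.1 could not alter how earlier events were recorded; the gain comes from the display.

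The cost is a few extra tables and one listing. A drug-related event wrongly attributed to progression would drop out of the reduced table, but it would remain in the full table and in the listing.

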7.5.2 Physical examination

A routine physical examination will be performed according to the visit schedule.

A full physical examination is to be performed once a month during the first five months of the study and every two months thereafter. It should comprise a total body examination (general appearance, skin, neck, including thyroid, eyes, ears, nose, throat, lungs, heart, abdomen, back, lymph nodes, extremities and basic nervous system).

Information about the physical examination must be present in the source documentation at the study site. Significant findings that are present prior to signing informed consent (or therapy) must be included in the Relevant Medical History / Current Medical Conditions CRF. Significant findings made after signing informed consent which meet the definition of an adverse event must be recorded on the Adverse Event CRF.

7.5.3 Vital signs

Pulse, blood pressure (measured after at least 3 minutes in the sitting position), temperature and weight will be measured at every visit. Height will be measured at baseline only.

Patients should be weighed and monitored regularly for signs and symptoms of fluid retention. An unexpected rapid weight gain should be carefully investigated and appropriate treatment provided.

7.5.4 Performance status

The patient's performance status should be estimated using the ECOG scale / Karnofsky scale, and recorded in the CRF. Post-text supplement 2 shows the grading scale for reference (Karnofsky, 1948).

7.5.5 Laboratory evaluations

Blood and urine samples will be analyzed in the local laboratory. The laboratory details will be provided in writing to Novartis prior to the screening of the first patient at the site. In particular, the name, address and contact details of the lab must be provided, together with the lab normal ranges, and a copy of the latest lab certificate. Unless prior agreement is given by

Novartis to the site, the site must use the same lab(s) for all samples from a given patient, and all patients at that site.

The following assessments should be made:

Hematology

Total white blood cell (WBC (total)), red blood cells (RBC), Hemoglobin, Hematocrit, platelets.

Differential counts of the following should be made also: neutrophils, lymphocytes, eosinophils, basophils, monocytes. Results should be provided as absolute or percentage values (not both). The same units used for the screening visit assessment should be used for all samples for a particular patient.

Blood chemistry

Urea or BUN (depending on what is commonly used at the site), creatinine, sodium, potassium, glucose, uric acid, LDH, total protein, albumin, total bilirubin, SGOT, SGPT, alkaline phosphatase, cholesterol, triglycerides γ -GT, Lipase, CRP, Quick, PTT.

Urine measurements

Glucose, protein, bilirubin, ketones, leukocytes, erythrocytes, specific gravity, pH, microscopic analysis.

